## APPENDIX 2. EASTERN COOPERATIVE ONCOLOGY GROUP PERFORMANCE STATUS

| Grade | ECOG   |
|-------|--|
| 0     | Fully active, able to carry on all predisease performance without restriction  |
| 1     | Restricted in physically strenuous activity but ambulatory and able to carry out work of a light or sedentary nature, eg, light housework, office work |
| 2     | Ambulatory and capable of all self-care but unable to carry out any work activities; up and about more than 50% of waking hours                        |
| 3     | Capable of only limited self-care, confined to bed or chair more than 50% of waking hours  |
| 4     | Completely disabled. Cannot carry on any self-care; totally confined to bed or chair   |
| 5     | Dead   |

Source: Oken et al, 1982.

## APPENDIX 3. RESPONSE CRITERIA

Table 12: PCWG3 Baseline Assessment of Disease – Amended for Trial SRF617-201

| Parameter                | Assessments   |
|--------------------------|---|
| Histology                | 

• Adenocarcinoma

• Excluded from Trial SRF617-201:

○ Adenocarcinoma with small-cell or neuroendocrine features

○ Small-cell carcinoma

• Report Gleason score sum for primary tumor at diagnosis, when available

• Consider re-biopsy of metastatic disease

 |
| Clinical                 | 

• Age, pain, analgesic use, performance status, comorbidities, history, physical examination; prior local therapy; TNM stage and Gleason score at diagnosis; and PSA

  |
| Prior systemic treatment | 

• Record each line of systemic therapy (single agent or combination) in order of administration, including start and stop dates, dose(s), and schedule(s), the disease state in which it was administered, and response (resistant versus sensitive) on the basis of PSA or radiologic findings, if appropriate

                           |
| Prior radiation therapy  | 

• Site, administered dose per fraction, treatment duration if applicable and when available

   |
| Blood-based biomarkers   | 

• Host: CBC with differential, ALP, kidney/liver function, albumin, LDH, testosterone

• Tumor: PSA and PSA kinetics (PSADT)a

   |
| Imaging                  |   |
| Prostate/Prostate bed    | 

• Endorectal MRI (cross-sectional imaging of prostate region, if applicable)

  |
| Nodal                    | 
CT or MRI:
 

• Nodes <math>\geq 1.5</math> cm in short axis are considered measurable; nodes <math>\geq 1.0</math> and <math>< 1.5</math> cm in short axis are considered pathologic according to clinical discretion, and nontarget; nodes <math>< 1.0</math> cm in short axis are considered nonpathologic

                   |

| Parameter   | Assessments   |
|---|---|
|   | 
 
Record pelvic and extra-pelvic nodal disease separately, up to 5 nodes in total; pelvic nodes should be classified as locoregional and extrapelvic (retroperitoneal, mediastinal, thoracic, or other) nodes as metastatic
 
Record new lesions vs growth of pre-existing lesions, and sites of new lesions
 
 |
| Visceral  | CT or MRI: 
 
Record individual sites of spread separately; up to 5 lesions per site
 
Lesions <math>\geq 1.0</math> cm in longest dimension are considered measurable
 
Record new lesions vs growth of pre-existing lesions, and sites of new lesions
 
  |
| Bone  | $^{99m}\text{Tc}$ MDP 
 
Record new lesions and sites of new lesions
 
   |
| Tumor profiling for determinants of prognostic, predictive, and resistance biomarkers | 
 
Consider re-biopsy of metastatic or locally recurrent lesion(s) for biologic characterization
 
Catalog prior biopsy (or cfDNA/ctDNA) genomic results
 
  |

Abbreviations:  $^{99m}\text{Tc}$  MDP =  $^{99m}\text{Tc}$  methylene diphosphonate; ALP = alkaline phosphatase; CBC = complete blood count; CEA = carcinoembryonic antigen; cfDNA = cell free DNA; CT = computed tomography; ctDNA = circulating tumor DNA; HRQoL = health-related quality of life; LDH = lactate dehydrogenase; MRI = magnetic resonance imaging; PCWG3 = Prostate Cancer Working Group 3; PSA = prostate-specific antigen; PSADT = prostate-specific antigen doubling time; TNM = tumor, node, metastasis.

a PSADT should be calculated using a linear regression model of the normal logarithm of PSA and time. The calculation should be based on (1) at least 3 consecutive PSA values with each value  $\geq 0.2$  ng/dL, (2) inclusion of the most recent PSA values during androgen deprivation therapy, and (3) interval between first and last PSA values of  $\geq 8$  weeks but  $\leq 12$  months.

Source: Scher, 2016.

Table 13: PWCG3 Criteria for Progression at Trial Entry

| Variable                             | Criteria  |
|--------------------------------------|---|
| Blood-based                          |   |
| PSA                                  | 
 
Obtain sequence of rising values at a minimum of 1-week intervals
 
1 ng/mL is the minimal starting value if confirmed rise is only indication of progression
 
If nonmeasurable disease, estimate pretherapy PSADT if <math>\geq 3</math> values available <math>\geq 4</math> weeks apart
 
   |
| Imaging                              |   |
| Nodes                                | 
 
Nodal progression sufficient for trial entry independent of PSA
 
Measurable lesions not required for entry
 
Modified RECIST v1.1 criteria, separate pelvic and extra-pelvic disease, up to 5 nodal lesions total recorded
 
Previously normal (<math>< 1.0</math> cm) lymph nodes must have grown by <math>\geq 5</math> mm in the short axis from Baseline or nadir and be <math>\geq 1.0</math> cm in the short axis to be considered to have progressed
 
If the node progresses to <math>\geq 1.5</math> cm in the short axis, it is measurable; nodes that have progressed to 1.0 to <math>< 1.5</math> cm are pathologic, subject to clinical discretion, and nonmeasurable
 
For existing pathologic adenopathy, progression is defined per RECIST v1.1
 
Record presence of nodal and/or visceral disease separately 
 
Nodal sites: 
 
Locoregional: pelvic only
 
Extra-pelvic: retroperitoneal, mediastinal, thoracic, or other
 
 
 
 
 
 |
| Viscera                              | 
 
Visceral progression sufficient for trial entry independent of PSA (recorded separately by site of spread [lung, liver, adrenal, CNS]); up to 5 lesions per site of metastatic disease
 
Measurable lesions not required for entry
 
Use RECIST criteria to record visceral lesions as target or nontarget
 
Record presence of nodal and/or visceral disease separately (visceral sites: lung, liver, adrenal, CNS)
 
   |
| Prostate/Prostate bed (primary site) | 
 
Record prior treatment of primary tumor (eg, surgery, radiation, cryoablation, radiofrequency ablation, none, other)
 
Perform directed pelvic imaging (CT, MRI, PET/CT, endorectal MRI, transrectal ultrasound) to document presence or absence of disease
 
  |

| Variable                           | Criteria   |
|------------------------------------|--|
| Bone                               | 

• 2 new lesions

• Confirm ambiguous results by other imaging modalities (eg, CT or MRI), but only positivity on bone scan defines metastatic disease to bone

   |
| Other sites of disease             | 

• Patients with treated epidural lesions and no other epidural progression are eligible

  |
| Type of progression at trial entry |  |
|                                    | 

• Report separately:

○ PSA only

○ Bone only <math>\pm</math> nodal disease

○ Nodal disease only (no bone disease present): pelvic and extrapelvic

○ Visceral (lung, liver, adrenal, CNS) disease (<math>\pm</math> other sites)

• Record new lesions and site of new lesions versus growth of pre-existing lesions, or both

 |

Abbreviations: CNS = central nervous system; CT = computed tomography; MRI = magnetic resonance imaging; PET = positron emission tomography;

PSA = prostate-specific antigen; PSADT = prostate-specific antigen doubling time; RECIST = Response Evaluation Criteria in Solid Tumors

Source: Scher, 2016.

**Table 14: RECIST Version 1.1 Lesion Response**

| Evaluation of target lesions    |   |
|---------------------------------|---|
| Complete response (CR):         | Disappearance of all extranodal target lesions. All pathological lymph nodes must have decreased to < 10 mm in short axis   |
| Partial response (PR):          | At least a 30% decrease in the sum of diameters of target lesions, taking as reference the Baseline sum of diameters  |
| Progressive disease (PD):       | At least a 20% increase in the sum of diameters of target lesions from the smallest value on trial (including Baseline, if that is the smallest). The sum of diameters must also demonstrate an absolute increase of at least 5 mm. Or, the appearance of one or more lesions |
| Stable disease (SD):            | Neither sufficient shrinkage to qualify for PR nor sufficient increase to qualify for PD  |
| Evaluation of nontarget lesions |   |
| Complete response (CR):         | Disappearance of all extranodal nontarget lesions, all lymph nodes must be nonpathological in size (< 10 mm in short axis), and normalization of tumor marker level   |
| Non-CR/non-PD:                  | Persistence of 1 or more nontarget lesion(s) or/and maintenance of tumor marker level above the normal limits   |
| Progressive disease (PD):       | Unequivocal progression of existing nontarget lesions. Or, the appearance of one or more lesions  |

Note: Evaluations for target, nontarget, and new lesions are to be considered together to assess an overall response status at a time point as detailed in [Table 15](#). For the overall response of CR or PR, confirmation of the response status at a subsequent time point at least 4 weeks apart from the initial observation is recommended.

Source: Eisenhauer et al, 2009.

**Table 15: Evaluation of Overall Response by RECIST Version 1.1**

| Target lesions    | Nontarget lesions           | New lesions | Overall response |
|-------------------|-----------------------------|-------------|------------------|
| CR                | CR                          | No          | CR               |
| CR                | Non-CR/non-PD               | No          | PR               |
| CR                | Not evaluated               | No          | PR               |
| PR                | Non-PD or not all evaluated | No          | PR               |
| SD                | Non-PD or not all evaluated | No          | SD               |
| Not all evaluated | Non-PD                      | No          | NE               |
| PD                | Any                         | Yes or no   | PD               |
| Any               | PD                          | Yes or no   | PD               |
| Any               | Any                         | Yes         | PD               |

Abbreviations: CR = complete response; NE = inevaluable; PD = progressive disease; PR = partial response/ remission, SD = stable disease.

Source: Eisenhauer et al, 2009.

11.6	Eastern Cooperative Oncology Group (ECOG) Performance Status	24
12	Other Analyses	25
12.1	Pharmacokinetic and Pharmacokinetic/Pharmacodynamic analyses.....	25
12.2	Pharmacodynamic Analyses	25
12.3	Immunogenicity Analyses	25
13	Interim Analyses.....	25
14	Statistical Analyses for Safety Monitoring.....	25
15	References	25

MODIFICATION HISTORY

Version	Version Date	Author	Changes from Previous Version
Final 1.0	29SEP2022	██████████	NA
Final 2.0	19JUN2023	██████████	Combined related TEAE to TEAE related to any drug; Kept summary of “Primary Composite Response Rate”, but removed other efficacy analyses; Removed the analysis sets that are not used in final analysis.

ABBREVIATIONS

ADA	Antidrug antibody
AE	Adverse Event
AESI	Adverse Event of Special Interest
BP	Blood Pressure
bpm	Beats per minute
CFB	Change from Baseline
CR	Complete Response
CRF	Case Report Form
CRO	Contract Research Organization
CSR	Clinical Study Report
CTCAE	Common Terminology Criteria for Adverse Events
CTMS	Clinical Trial Management System
DCR	Disease control rate
DoR	Duration of Response
ECG	Electrocardiogram
ECOG	Eastern Cooperative Oncology Group
EoT	End of Treatment
iv	Intravenously
MedDRA	Medical Dictionary for Regulatory Activities
mCRPC	Metastatic Castration-Resistant Prostate Cancer
mg	milligram
mL	milliliter
mmHg	millimeter of mercury
NCI	National Cancer Institute
NE	Not Evaluable
ng	nanogram
ORR	Objective Response Rate
PAP	Prostatic Acid Phosphatase
PCWG	Prostate Cancer Working Group
PD	Progressive Disease
PD-L1	Programmed Death-Ligand 1
PDMP	Protocol Deviations Management Plan
PFS	Progression Free Survival
PK	Pharmacokinetics
PN	Preferred Name
p.o.	per os , by mouth
PR	Partial Response
PSA	Prostate-Specific Antigen
PSA ₃₀	At least 30% decline in PSA
PSA ₅₀	At least 50% decline in PSA
PT	Preferred Term
q2w	Once every 2 weeks
q4w	Once every 4 weeks
q.d.	quaque die , once a day
QTc	Heart rate-corrected QT interval
QTcF	QT Interval corrected with Fridericia's method
RECIST	Response Evaluation Criteria in Solid Tumors

SAE	Serious Adverse Event
SAP	Statistical Analysis Plan
SD	Standard Deviation
SOC	System Organ Class
SRC	Safety Review Committee
SSE	Symptomatic Skeletal Event
TEAE	Treatment Emergent Adverse Event
TLF	Tables, Listings, and Figures

1 INTRODUCTION

The objective of this document is to detail the statistical methodology to be used in the statistical analyses of clinical protocol SRF617-201 “A Phase 2 Trial of SRF617 in Combination With AB928 (Etrumadenant) and AB122 (Zimberelimab) in Patients With Metastatic Castration-Resistant Prostate Cancer” Amendment 1.1 dated on 30JUL2021) and Patient Case Report Forms (CRFs version 3.0 dated on 19MAY2022)

Pharmacokinetics and pharmacodynamics analyses, with the exception of data summaries, and reporting are not included in this analysis plan.

1.1 Discrepancies Between the SAP and the Protocol

Surface (sponsor) terminated the study when 15 subjects received treatment. The abbreviated analysis will focus on safety assessments.

Pharmacokinetics Analysis Set, Blood Biomarker Analysis Set, Tumor Biopsy Analysis Set, and Immunogenicity Analysis Set, and corresponding analyses are removed from this SAP.

2 STUDY DESIGN

This is a Phase 2, open-label, safety and preliminary efficacy trial in patients with mCRPC who have progressed on or after prior ARSI therapy. The study will employ a 2-stage design with an integrated safety lead-in for the triplet combination of SRF617, etrumadenant, and zimberelimab.

Stage 1 will enroll *approximately* 17 patients, including the Safety Lead-in that will initially treat 6 patients. After the first 6 patients have been enrolled, enrollment will be paused until these patients have received 1 cycle of the triplet combination and the Safety Review Committee has reviewed the aggregate safety data. Once the SRC deems it safe to proceed, an additional 11 patients will be enrolled.

Based on an evaluation of safety and response data, the trial will proceed to the Stage 2 expansion if ≥ 1 radiographic complete response (CR)/partial response (PR) or prostate-specific antigen (PSA) responses (defined as a $\geq 50\%$ decline [PSA₅₀]) according to the Prostate Cancer Working Group 3 (PCWG3) criteria are observed in 17 evaluable patients. An additional 23 patients will be enrolled in Stage 2 for further evaluation of the safety and efficacy of the combination. At the end of Stage 2, at least 8 responses (radiographic responses or PSA response) are needed to claim preliminary efficacy of the study treatment.

Tumor biopsies are optional; they will be performed to explore potential biomarkers of response to the combination in patients who consent to the procedure, who have non-bone metastases amenable to biopsy, and for whom the procedure is deemed safe.

Patients will continue to receive study drug for up to 2 years or until documented disease progression or unacceptable toxicity. Patients may remain on study drug longer than 2 years with agreement from the trial Investigator and Sponsor.

In November 2022, the Sponsor announced that development of SRF617 would be discontinued. Patients enrolled and/or consented for treatment on SRF617-201 were permitted to continue treatment per study protocol, but additional patients were not enrolled. Importantly the decision to discontinue development of SRF617 was a business decision; there were no safety concerns. As of 19JUN2023, 15 subjects received treatment.

2.1 Study Objectives and Endpoints

Primary Objectives	Primary Endpoints

 To evaluate the preliminary efficacy of SRF617 administered in combination with etrumadenant and zimberelimab as determined by objective response and PSA decline To evaluate the safety and tolerability of the combination 	
 The proportion of patients with a response, defined as PSA₅₀ response ($\geq 50\%$ decline) and/or radiographic objective response of CR or PR per PCWG3 criteria Incidence and severity of AEs
Secondary Objectives	Secondary Endpoints

 To evaluate additional preliminary efficacy parameters of the combination including objective response rate (ORR), PSA response, clinical benefit, duration of response, and radiologic progression-free survival (PFS) To evaluate the PK of SRF617 when administered in combination with etrumadenant and zimberelimab To characterize additional safety parameters including development of antidrug antibodies (ADAs) and symptomatic skeletal events (SSEs) 	
 ORR per PCWG3 criteria, ORR per Response Evaluation Criteria in Solid Tumors (RECIST) v1.1, duration of response, disease control rate, PSA₅₀ response, PSA decline $\geq 30\%$ (PSA₃₀) response, time to PSA progression, radiographic PFS, and landmark PFS rate at 6 and 12 months Serum concentrations of SRF617 Percentage of patients with ADAs to SRF617 Incidence of SSEs
Exploratory Objectives	Exploratory Endpoints

 Explore potential biomarkers of response and/or safety of the combination Explore the effects of the triplet on peripheral blood immune cell subsets and circulating serum cytokines and chemokines Explore the biological effects of the triplet on tumor cells and immune cell populations in the tumor microenvironment Explore germline DNA polymorphic variations in relation to the PK, pharmacodynamics, safety, and/or preliminary efficacy Explore correlations between prostate cancer biomarkers in tumors with biomarkers in serum in patients who undergo tumor biopsy Explore correlations between prostate cancer biomarkers in tumors with clinical response parameters in patients who undergo tumor biopsy 	
 Changes in selected blood and tumor tissue biomarkers Germline DNA polymorphic sequence variations in relation to the PK, pharmacodynamics, safety, and/or preliminary efficacy of SRF617 Serum prostatic acid phosphatase (PAP) levels PAP expression levels in tumors in patients who undergo tumor biopsy Programmed death-ligand 1 (PD-L1) and CD39 expression levels in tumors in patients who undergo tumor biopsy

2.2 Study Treatment

Treatment cycles are 28 days in duration.

Study Drug	Dosing Route and Schedule	Initial Dose	1st Reduction	2nd Reduction
SRF617	iv q2w on Days 1 and 15 of each cycle	1400 mg	700 mg	350 mg
Etrumadenant	orally at a daily dose	150 mg	100 mg	75 mg
Zimberelimab	iv q4w on Day 1 of each cycle	480 mg	NA	NA

2.3 Sample Size Considerations

This trial will enroll approximately 40 patients. A patient is enrolled in the trial after they have provided informed consent and met all trial eligibility criteria.

A 2-stage design will be implemented. Stage 1 will include a 6-patient Safety Lead-in followed by enrollment of an additional 11 patients for a total of 17 patients. At least 1 radiographic CR/PR or 2 PSA₅₀ responses by PCWG3 criteria out of 17 evaluable patients must be observed in order to consider opening Stage 2, which will enroll an additional 23 patients for further evaluation of the safety and efficacy of the triplet. The trial will have met its primary endpoint if at least 8 patients in total achieve a response.

The sample size for this triplet combination therapy dose expansion is based on a null hypothesis of a 10% composite response rate (PSA₅₀ or CR/PR) with PD-1 blockade alone versus the alternate hypothesis that the composite response rate is 30%, with a calculated alpha of 0.040 and power of 0.93.

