3.4 Response-Evaluable Analysis Set

The Response-Evaluable Analysis Set is defined as all enrolled patients who received SRF617 and had at least 1 post-Baseline response assessment (including PSA assessment and/or tumor assessment) or who discontinued the treatment phase because of radiographic or symptomatic disease progression (including death caused by disease progression) within 6 weeks (+ 2-week window) of the first dose of SRF617. This analysis set will be the primary analysis set for the primary efficacy endpoint and other efficacy endpoints.

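### Does SAP 2.3 need changing because it still gives alpha 0.040 and power 0.93 for about 40 patients, when the trial stopped at 15 treated?

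*SAP*

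**What the plan says.** SAP 2.3 sets out the sizing of the trial: "This trial will enroll approximately 40 patients", 17 in Stage 1 and 23 in Stage 2, with a null composite response rate of 10% and an alternative of 30%. The success rule is "The trial will have met its primary endpoint if at least 8 patients in total achieve a response", and the design is described "with a calculated alpha of 0.040 and power of 0.93". This follows Protocol 9.1 closely.

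Other sections of the same SAP version record what happened. SAP 1.1 says the sponsor "terminated the study when 15 subjects received treatment" and that the shortened analysis concentrates on safety. SAP 2 says patients already enrolled or consented could continue, "but additional patients were not enrolled", and that the reason was a business decision. SAP 2 also ties the success rule to a time point: "At the end of Stage 2, at least 8 responses" are required. SAP 13 records that Stage 2 was not opened and that the end-of-Stage-1 analysis becomes the final one.

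On efficacy, the modification history says Final 2.0 kept the composite response rate "but removed other efficacy analyses". SAP 10.2.1 reports that rate with two-sided 80% and 95% Clopper-Pearson intervals and a one-sided exact p-value against 10%. It gives no significance level. The denominator is the response-evaluable set of SAP 3.4. Patients enter that set if they received SRF617 and "had at least 1 post-Baseline response assessment (including PSA assessment and/or tumor assessment"), or if they stopped early for progression.

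**The concern.** Final 2.0 was a deliberate cut-down after termination, yet Section 2.3 remains in the future tense and unmarked. The composite response rate and its test against 10% survived the cut, so the only alpha and power in the SAP sit beside a live test to which they do not belong.

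Two misreadings are possible. A p-value that is not small could be reported as a negative result from a trial with 93% power. A borderline result could be judged against whichever level suits, because neither SAP 4.2 nor SAP 10.2.1 states one or calls the p-value descriptive. The sensitive count is 4 responders, which is 27% of 15 or 31% of 13 and so close to the 30% target. There the p-value lies between 0.03 and 0.06, and the 80% and 95% intervals fall on opposite sides of 10%.

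**Working it through.** **Inputs.** From SAP 2.3: null rate 10%, alternative 30%, stages of 17 and 23, success at 8 or more of 40. From SAP 1.1 and 2: 15 treated. The documents do not give the response-evaluable number or a level for the SAP 10.2.1 test. I therefore assume 13 to 15 evaluable patients (15 is the ceiling) and one-sided levels of 0.025 to 0.05, with 0.10 shown for comparison.

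**Step 1: reproduce the plan's figures.** With a gate of at least 2 responders in Stage 1,

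P(success | p) = Σ (x = 2 to 17) Bin(x; 17, p) × P[Bin(23, p) ≥ 8 − x].

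- p = 0.10 gives 0.0399, printed as 0.040.
- p = 0.30 gives 0.934, printed as 0.93.

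Both agree. The gate as written admits one radiographic response or two PSA50 responses. Depending on the share of responders who are radiographic, it gives 0.0399 to 0.0417 and 0.934 to 0.944, which is not materially different.

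**Step 2: the test at the sample size reached.** For n evaluable patients, the critical count r is the smallest with P[Bin(n, 0.10) ≥ r] no greater than the level. Power is P[Bin(n, 0.30) ≥ r].

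| n | One-sided level | r | Size | Power at 30% |
|---|---|---|---|---|
| 15 | 0.025, 0.040 or 0.05 | 5 | 0.0127 | 0.485 |
| 15 | 0.10 | 4 | 0.0556 | 0.703 |
| 14 | 0.025 or 0.040 | 5 | 0.0092 | 0.416 |
| 14 | 0.05 or 0.10 | 4 | 0.0441 | 0.645 |
| 13 | 0.025 | 5 | 0.0065 | 0.346 |
| 13 | 0.040, 0.05 or 0.10 | 4 | 0.0342 | 0.579 |

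For levels 0.025 to 0.05 the range is 0.346 to 0.645. Its ends come from different assumptions: 13 patients at 0.025, and 14 patients at 0.05. At 15, the only count the SAP gives, power is 0.485 at every level in that range.

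**Step 3: the borderline result.**

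| Result | One-sided p | 80% CI | 95% CI |
|---|---|---|---|
| 4/15 | 0.056 | 12.2% to 46.4% | 7.8% to 55.1% |
| 4/14 | 0.044 | 13.1% to 49.2% | 8.4% to 58.1% |
| 4/13 | 0.034 | 14.2% to 52.3% | 9.1% to 61.4% |

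Clopper-Pearson limits invert the one-sided exact tests. The 80% lower limit lies above 10% when p is below 0.10, and the 95% lower limit when p is below 0.025. All three rows have p between 0.025 and 0.10, so the 80% interval excludes 10% and the 95% interval includes it. The p-value therefore says nothing that the two planned intervals do not already show.

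**Step 4: could the old success rule be applied by mistake?** Eight or more responders among 15 has probability 0.050 at a 30% rate. SAP 2 places the rule at the end of Stage 2 and SAP 13 says Stage 2 was not opened, so the rule has lapsed on the SAP's own terms.

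**The case for a change.** The best argument for a change is that the efficacy test was kept on purpose. The revision removed the other efficacy summaries but left this one, with the same 10% null that Section 2.3 uses. If a test stays in the plan, its level should be fixed before the results are read. At 14 evaluable patients, 4 responders give p = 0.044, which is below 0.05 but above the printed 0.040. Section 2.3 does not itself repeat that the success rule belongs to the end of Stage 2, and a concentration on safety does not make a p-value descriptive. A few words would settle all of this at no cost.

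Part of this stands. The figures in Section 2.3 carry no label as the original design, and Section 10.2.1 does not say how its p-value is to be read.

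The rest carries less weight:

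- The 0.040 is the calculated error rate of the 17+23 rule, not a cut-off for the p-value in SAP 10.2.1, so the 4/14 comparison sets two unrelated quantities against each other.
- SAP 1.1 lists departures from the protocol. Section 2.3 agrees with Protocol 9.1 and so has none to list; the real departure, the early stop, is there.
- SAP 2 uses the same layout, giving the design as planned and then a paragraph on termination.
- Enrolment is closed and development has been discontinued, so power at the number reached can guide no decision. The exact intervals show the precision obtained.

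**Conclusion.** The concern is accurate about what is printed but does not call for a change. Section 2.3 records the basis on which the trial was sized, and its figures are correct for that design. They do not describe the final analysis, and the same SAP says plainly that the trial stopped at 15 treated and did not reach Stage 2. There is no contradiction and no wrong calculation, only a missing label.

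Power for the retained test is well below 93%: 48.5% with 15 evaluable patients, and 35% to 64% across the assumed 13 to 15 patients and one-sided levels of 0.025 to 0.05. That loss comes from stopping early and cannot be recovered by wording. Followed as written, the plan gives one response rate, two exact intervals and one p-value, with no rejection rule and no success claim still available. A statistician reporting it would treat the p-value as descriptive and rely on the intervals. Relabelling would leave every reported number as it is.
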